**Version Revision History:**

Version #	Version Date	Summary of Revisions Made:
0.1	28 March, 2019	Initial draft
1.0	23 April, 2019	IRB Approval
1.1	3 May, 2019	Section 13.2.1 Quality Assurance Procedures was updated. Section 15.2 Data Collection Methods and Organization of the Data was updated.
2.0	3 May, 2019	PCORI Methodology Standards were added
3.0	18 October, 2019	PCORI Program Officer information updated, Key Personnel updated (removed [name] and added [name]). Sections 7.1, 7.2, 7.3, 8.1.1, 9.2 and Figure 15.3.1 were updated to add the Safety Questionnaire (Pre-Exam).
4.0	28 October, 2019	Sections 6.2 and 6.10 were updated to indicate that a rotary brush will not be used for the ART treatment procedure, only a manual brush. Sections 6.10, 7.1 and 7.2 were updated to outline procedures for addressing participant reported issues with the applied treatment.
5.0	11 November 2019	Sections 4.1 and 5 have been revised to add severe cognitive impairment as an exclusion criteria at the recommendation of the study's Data and Safety Monitoring Board. Revisions have been made to section 5 to clearly outline the screening and enrollment process for the study.
6.0	3 April 2020	Section 7 (Study Schedule) has been revised to add temporary COVID-19 procedures for obtaining written informed consent and collecting survey data at baseline and 26-week follow-up.
7.0	17 June 2020	Section 7 (Study Schedule) has been revised to add temporary COVID-19 in-person procedures for recruitment, data collection and dental screening/treatment. Section 1 has been updated with the current name and contact information for the PCORI Program Official and Key Personnel.
8.0	10 August 2020	Section 7 (Study Schedule) has been revised to include that study exams/treatment during temporary COVID-19 in-person visits may take place in an outside location at the facility if requested by housing site personnel.

9.0	9 October 2020	Section 7 (Study Schedule) has been revised to be consistent with current screening guidelines indicating that individuals with a self-reported or on-site screening temperature > 100.0, will not be scheduled nor seen for a study visit or exam/treatment. Previously, the cut-off temperature was 100.4. Section 7.2 and 7.3 have been revised to correct the window timeframes.
10.0	13 November 2020	Section 7 (Study Schedule) has been revised to include remote data collection for questionnaires at the 52-week follow-up visit rather than in-person during the COVID-19 pandemic. Section 7.3 has been updated to include administration of the COVID-19 dental visit questionnaire at the 52-week follow-up visit, and section 6.11 has been corrected to indicate the proper arms.
11.0	29 September 2021	Updates have been made to the PCORI program official name and contact information. The Protocol Summary and sections 4, 5, 7.3 and 8.1.2 have been updated to reflect PCORI approved modifications to the study timeline (+18 months), # to be enrolled (+40) and # of facilities (+4) to address COVID-19 challenges. Section 8.1.2 has also been updated to indicate that focus groups may be conducted at a housing site or virtually based on housing site circumstances at the time of scheduling.
12.0	16 June 2022	Section 1: Study Sites was updated to add Educator Senior Housing.
13.0	4 Oct 2022	Section 1: Study Sites was updated to add Lorain Square and Beachcrest.
14.0	11 April 2023	The Protocol Summary was updated to reflect the correct # of added sites. Section 1: Study Sites and Section 4.1: Facility Table were updated to add all sites where recruitment/enrollment was completed. Key Roles and Contact Info. was updated to add [name] as the Research Associate. Sections 6.8 and 6.11 were updated to reflect that the study dentist may not be present at 52 week follow-up visits where treatment is not delivered. Section 7.3 was updated to reflect that the dentist or hygienist will administer the Safety Questionnaire (pre-exam) at the 52-week follow-up visit.

## **STATEMENT OF COMPLIANCE**

The study will be conducted in accordance with the International Conference on Harmonisation guidelines for Good Clinical Practice (ICH E6), the Code of Federal Regulations on the Protection of Human Subjects (45 CFR Part 46), and the PCORI Contract for funded research project. All personnel involved in the conduct of this study have completed human subjects protection training.

---

## LIST OF ABBREVIATIONS

AE	Adverse Event/Adverse Experience
ACA	Affordable Care Act
ADA	American Dental Association
ART	Atraumatic Restorative Treatment
CRF	Case Report Form
CWRU	Case Western Reserve University
CHAID	Chi-Squared Automatic Interaction Detection
CART	Classification And Regression Trees
CONSORT	Consolidated Standards Of Reporting Trials
DSMB	Data Safety And Monitoring Board
DHHS	Department of Health and Human Services
EQUATOR	Enhancing the QUAlity and Transparency Of health Research
FV	Fluoride Varnish
GEE	Generalized Estimating Equations
GOHRQoL	Geriatric Oral Health Quality Of Life
GIC	Glass Ionomer Cement
GCP	Good Clinical Practice
HIPAA	Health Insurance Portability and Accountability Act
HUD	Housing And Urban Development
IRB	Institutional Review Board
ICDAS	International Caries Detection And Assessment System
ICMJE	International Committee of Medical Journal Editors
ICH	International Conference On Harmonisation
ICC	Intraclass Correlation
IDE	Investigational Device Exemption
IDE	Investigational Device Exemption
IND	Investigational New Drug
IND	Investigational New Drug Application
MCAR	Missing Completely At Random
NCOA	National Council On Aging
NHANES	National Health And Nutrition Examination Survey
NIH	National Institutes Of Health

[figure not shown]
NIH	National Institutes of Health
NDA	New Drug Application
PCORI	Patient-Centered Outcomes Research Institute
PROMIS	Patient-Reported Outcomes Measurement Information System
PI	Principal Investigator
PHI	Protected Health Information
QA	Quality Assurance
QC	Quality Control
RCT	Randomized Clinical Trail
REDCap	Research Electronic Data Capture
SAE	Serious Adverse Event/Serious Adverse Experience
SDF	Silver Diammine Fluoride
SOP	Standard Operating Procedure
SPIRIT	Standard Protocol Items: Recommendations For Interventional Trials
TSQM	Treatment Satisfaction Questionnaire For Medication
UP	Unanticipated Problem
US	United States
VAS	Visual Analogue Pain Scale
WHO	World Health Organization
WHO	World Health Organization
ZINB	Zero-Inflated Negative Binomial
ZIP	Zero-Inflated Poisson

## PROTOCOL SUMMARY

Title:	Reducing Oral Health Disparities of Older Adults: Comparative Effectiveness of 2 Treatments
Précis:	The study is a cluster randomized clinical trial (RCT) to be conducted in 22 publicly subsidized housing facilities/sites (HUD Section 202) and other low-income housing voucher programs in NE Ohio. The facilities will be randomized to 2 arms: Arm 1 (11 sites) – Participants will receive biannual silver diamine fluoride (SDF) versus Arm 2 (11 sites): Participants will receive atraumatic restorative treatment (ART) with glass ionomer cement (GIC) + biannual fluoride varnish (FV) application. A total of 550 participants (Arm 1: 275, Arm 2: 275) will be followed for one year.
Objectives:	
Primary: To compare the effectiveness of two evidence-based strategies, a “simple medical” strategy of topical application of SDF versus a “typical dental” strategy consisting of ART + FV given to older adults 62 and older to address (1) participant reported outcomes including tooth pain and hypersensitivity; and (2) clinical outcomes (caries arrest).
 
Secondary: To assess (1) participant reported outcomes (oral health quality of life, safety, and patient satisfaction); and (2) clinical outcomes (prevention of new decay).

Population:	
Population information: sample size = 550 older adults to be randomized; participants aged <math>\geq</math> 62 years will be recruited from 22 subsidized housing facilities in NE Ohio, and will be randomized if they have at least one untreated active root or coronal carious lesion, and are willing to be in the study for 1 year. The socio-demographics of this population is expected to be a mean age of 74 years, 76% female, 51% Caucasian, 45% African-American, 2% Hispanic, and 2% other groups, 83% with two or more medical conditions.
 
Due to COVID-19 restrictions which prevented outside visitors/providers at the housing sites, approximately 40 enrolled individuals did not complete the 26 week visit/second dose of treatment. We will therefore increase the total number of enrolled participants by 40.

Phase:	III
Number of Sites:	22 independent living facilities for older adults, plus an additional 11 housing facilities to address some delays in recruitment due to the COVID-19 pandemic.
Description of Intervention:	
The interventions for this study are in current clinical use. Two evidence-based strategies in older adults will be compared as follows: (Arm 1) a “simple medical strategy” consisting of SDF versus (Arm 2) a “typical dental strategy” consisting of ART + FV. We will attempt blinding of participants to the study group, but may not be possible due to SDF color change.
 
The protocol for each arm will address both coronal and root surface tooth decay lesions: Arm 1: The treatment will be bi-annual topical 38% silver diamine fluoride (Advantage Arrest, Elevate Oral Care LLC., West Palm Beach, FL) following manufacturer's instructions and guidelines published by UCSF; Arm 2: Atraumatic Restorative Treatment (ART) will be a modification of the approach used by Lo and colleagues (2006), and the cavity restored with high viscosity glass-ionomer cement (GIC) (GC Fuji Automix LC Resin Reinforced Glass Ionomer Restorative, Japan)). Patients will also receive biannual topical fluoride varnish treatments (FluoriMax, Elevate) according to manufacturer's instructions.

Study Duration:	48 months
Subject Participation Duration:	12 months
Estimated Time to Complete Enrollment:	26 months

## 2 INTRODUCTION: BACKGROUND INFORMATION AND SCIENTIFIC RATIONALE

### 2.1 Background Information

The current U.S. health care system does not treat comprehensive dental care for adults as an essential health benefit under the ACA (**RQ-1**). Medicare excludes dental care and particularly for low-income individuals it leaves them with high out-of-pocket costs: 74% of the beneficiaries do not receive dental care annually. The Institute of Medicine (IOM) recognizes that preventive oral care can reduce medical costs.

Over 96% of all U.S. older adults aged  $\geq 65$  years have had caries experience in the permanent teeth. Untreated tooth decay is disproportionately found in non-Hispanic Black (41%) and Hispanic (27%) compared to non-Hispanic white older adults (16%). Consequently, tooth loss is also significantly higher in non-Hispanic blacks compared to other groups. About 37% of adults  $\geq 65$  years have tooth decay in exposed root surfaces. Caries is the primary cause of tooth loss in older adults, and tooth loss is inversely related to oral health related quality of life. The progression of oral diseases adversely affects general health. A recent 2018 oral health screening and survey of older adults highlights that many are living with significant untreated dental disease especially low-income seniors impacting their chewing, nutrition, and overall wellbeing that requires immediate attention and focus (**RQ-1**).

Our 2016-17 data on 202 older adults from 16 publicly subsidized housing units indicates untreated caries (58%) is two times higher than the national average (28%). All had at least one medical condition, while 83% had two or more medical conditions (**RQ-4**). Nationally, 92% of U.S. older adults have at least one medical condition, and 77% have  $\geq 2$  conditions. Low-income U.S. older adults have disproportionately increased medical conditions compared to their more affluent counterparts as shown by our NE Ohio data. Recent studies indicates that poor dental health (caries, periodontitis) was related to worsening glucose tolerance and an increased risk of diabetes, and having fewer teeth/tooth loss and other patient reported oral health problems was associated with greater physical frailty in older adults. Medical conditions lead to less frequent dental visits among older adults with cognitive impairment and those with diabetes, with significant disparities among low-income groups. Moreover, systemic conditions such as cardiovascular and respiratory disease, diabetes etc. have been associated with oral infections. Untreated oral infection leads to pain, overuse of emergency visits, and even death (**RQ-1**).

Despite the profound impact of oral health status on quality of life, many older adults accept their oral health problems as an inevitable process of aging and do not seek dental care. In fact, ADA Health Policy Institute survey indicates that low perceived need (i.e. not needing dental care) was the top reason that older adults do not intend to visit a dentist. This belief, further impacted by limited dental insurance options results in oral health becoming a low priority among older adults. The National Health Interview Survey 2014 data indicate that most older adults reported financial barriers to receiving dental care compared to any other type of health care. A further challenge is that older adults have increased medical problems, physical frailty, and cognitive issues that challenge dental care access in this group. Testing interventions provided outside of traditional dental offices will address barriers to seeking care among this population (**RQ-1, RQ-3**).

Conventional restorative treatments do not work for older adults. The dental treatment needs of older adults differ from those of younger adults and thus makes diagnosis and treatment planning more complex due to age related changes to the enamel, dentine, and pulp chamber. For this reason, results of work conducted in children cannot be extrapolated to older adults (**RQ-1**). The majority of tooth decay in older adults is failure of restorations at the gum line and in exposed roots. These lesions are difficult to diagnose or restore, even for experienced dentists. A randomized trial in older adults with root caries treated the decayed tooth surfaces with either ART or conventional treatment (using a dental drill) and found that ART had a similar restoration survival rate (87% vs. 91%). Fluoride varnish and SDF are also both effective in arresting and preventing new tooth lesions.

Silver Diamine Fluoride (SDF) has been long used to arrest caries in other countries and is now widely available in the United States. The liquid agent is painted on the decayed tooth or root and the treated lesion hardens, while the lesion depth decreases and becomes resistant to caries bacteria. SDF inhibits the decay process by restricting the bacterial metabolic and reproductive functions leading to bacterial killing. Thus, silver is an antimicrobial that kills cariogenic bacteria far superior to other antimicrobial medicaments. Annual 38% SDF has been effective in arresting and preventing root caries lesions among older adults in clinical trials. Recently, the American Dental Association evidence-based clinical practice guidelines recommends bi-annual application of SDF on permanent teeth.

Despite the greater dental caries burden, there are no community-based public health interventions that exist for low-income older adults like those for children, and the current clinic-based dental care delivery system is expensive and ill adapted (**RQ-1**). For any caries preventive/treatment intervention to be useful on a population level, 5 presumed attributes are necessary: pain and infection control, simplicity of use, cost affordability, minimal personnel time and training, and non-invasive. Our proposed non-surgical interventions can meet this criteria and provide evidence (**RQ-5**).

Therefore, we propose a cluster RCT to compare two non-surgical evidence-based strategies to address disparities in untreated tooth decay and dental care access (**RQ-2**). The conventional surgical care using the “drill” and “fill” paradigm is not the best nor the most effective option for low-income older adults. Nationally, if only 26% of Medicare beneficiaries are seeking dental care annually in dental offices, our proposed interventions has the potential to reach a lot more older adults where they live in order to reduce oral health disparities.

## 2.2 Rationale

Comparative effectiveness studies of the proposed interventions are needed to inform the most effective community-based treatment strategy for older adults and to establish a standard of care (**RQ-1, SR-1**). A systematic review and meta-analysis supports the use of SDF, the use of ART with high viscosity glass ionomer cements (GIC), and the use of fluoride varnish (FV) for tooth decay management in older adults (**RQ-5**). Thus, the proposed research compares commonly used evidence-based treatments.

Therefore, this study will determine the effectiveness of two relatively inexpensive, accepted non-surgical treatments that can be provided by dental hygienists (dental paraprofessionals) in

most states outside of traditional dental clinics to address the unique oral health needs of low-income older adults (**RQ-1**) i.e. a “simple medical” strategy using bi-annual application of SDF and a “typical dental” more complex strategy consisting of ART and biannual application of FV. The rationale is that providing conventional (surgical with a drill) treatment actually exacerbates disparities because such treatment is resource intensive and is relatively ineffective. Our hypothesis tests that the “medical” strategy is not less effective as the “dental” strategy in caries arrest and prevention.

Further, our focus is on low-income older adults residing independently in Housing and Urban Development (HUD) and other publicly subsidized housing facilities with limited access to dental care. In particular, we will focus on subgroups of older adults with co-existing medical conditions as these individuals are most likely to experience disparities (**RQ-4**). The non-surgical treatment strategies were selected based on scientific evidence and the feasibility of application by licensed paraprofessionals in community-based settings as this can address multiple barriers to dental care and subsequently increase access for low-income older adults (**RQ-5**). Both approaches are now used in traditional dental clinics along with conventional intensive dental care. Our outcomes address the concerns of older adults (based on surveys, interviews, and prior studies of this population) that include: tooth decay, and participant reported tooth pain, hypersensitivity, and decreased quality of life (**RQ-3, RQ-6, PC-1**).

## 2.3 Potential Risks and Benefits

### 2.3.1 *Potential Risks*

Study Interventions: SDF was introduced in the US in 2015 and approved by the FDA as a medical device; the high viscosity glass ionomer cements (GIC) used in ART were introduced in the 1970s. All of the interventions are in current clinical use for package inserts for SDF, ART with GIC, FV). The study interventions are non-invasive and does not require the use of conventional drilling procedures. There is risk of hypersensitivity to silver or fluoride from the 38% SDF. SDF can stain the gums or oral mucosa or tooth colored fillings. There is minimal risk with the ART and FV applications (**RQ-5**).

Dental exams: The project will involve clinical dental exams for the participants. The dental exams do not pose any additional risks to participants beyond those encountered in daily living. Dental examinations will be visual/tactile using a probe and non-invasive. No x-rays will be taken.

Interviews: Some people are uncomfortable answering questions about themselves for research. We will try to make participants feel as comfortable as possible. There is also a chance that confidential information can be lost but we will use every precaution to protect the information. To protect the privacy of participants, a unique ID number will be used. The connection between this code number and participant’s identity will be confidential and will be required to link the contact form, questionnaires and dental data. Only project staff members will have access to these codes and identifying information. Once the study data collection is completed, the link between the individual and their data will be destroyed.

Focus groups: There is little risk to participants during the focus group discussions. While it is unlikely, some participants may feel shy or embarrassed by some of the questions asked during the meetings or interviews. The facilitator and moderator will make every effort to put participants at ease and to communicate to them that any information shared during the discussions and interviews would not be relayed to others. Further, any names or other identifying information will be removed during the transcription process and will not appear in the final transcripts of the discussion groups. All audio files will be deleted after they are transcribed.

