### 4.1 Study Participants (RQ-3, RQ-4, PC-2)

Subjects will be low socioeconomic status (SES) adults  $\geq 62$  years of age in NE Ohio counties (Cuyahoga, Lorain, Summit, Ashtabula, Geauga, and Lake) residing in 22 participating HUD Section 202 and other publicly subsidized housing facilities (see table 1). The population is diverse: African American/Black, Caucasian/White including Hispanic/Latino, and Asian. Medicaid participation among the tenants is 76% among facilities. From our prior study in these facilities, mean age is 74 years, 76% female, 51% Caucasian, 45% African-American, 2% Hispanic, and 2% other racial/ethnic groups; 60% of HUD older adults had none/rare dental visits in over 3 years. The study will be offered to all older adults if they are aged  $\geq 62$  years, reside in the 22 housing facilities, have at least one natural tooth and be willing to stay in the

study for 1 year. Only those with severe medical, cognitive or motor impairments will be excluded. To be eligible for enrollment in the clinical trial phase of the study, at the baseline dental exam, subject must have at least one untreated active root or coronal carious lesion with ICDAS-II lesion severity code of 3 or greater.

Table 1. Facilities Enrolled in the Clinical Trial				
Facility Name*	# of tenants	Name of Individual Providing Letter of Support (Agency)	Type of Community	County
Westerly Apartments	455	[name] (Westerly Apartments)	suburban	Cuyahoga
St. Timothy Manor	40	[name] (Humility of Mary Housing)	suburban	Cuyahoga
St. Timothy Park	40	[name] (Humility of Mary Housing)	suburban	Cuyahoga
Villa at Marion Park	40	[name] (Humility of Mary Housing)	urban	Summit
St. Patrick Manor	50	[name] (Humility of Mary Housing)	suburban	Lorain
Jennings Manor, Library Court, St. Rita, St. Agnes	220	[name] (Jennings)	suburban	Cuyahoga
Margaret Wagner	60	[name] (Benjamin Rose Institute)	urban	Cuyahoga
Willowood Manor	74	[name] (Willowood Manor)	suburban	Cuyahoga
Knickerbocker	168	[name] (Knickerbocker)	suburban	Cuyahoga
Abington Arms	157	[name] (Abington Arms)	urban	Cuyahoga
Fedor Manor	145	[name] (Fedor Manor)	suburban	Cuyahoga
Ambleside Tower	201	[name] (CMHA)	urban	Cuyahoga
Severance Tower	188	[name] (CMHA)	urban	Cuyahoga
Cedar Highrise	155	[name] (CMHA)	urban	Cuyahoga
Addison Square	225	[name] (CMHA)	urban	Cuyahoga

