##### **Arm 1 (N=275 participants): A “simple medical strategy” consisting of SDF**

The treatment will be bi-annual application (at baseline and 26 weeks) of topical 38% silver diamine fluoride (Advantage Arrest, Elevate Oral Care LLC., West Palm Beach, FL) following manufacturer's instructions and guidelines published by UCSF.

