##### **Arm 2 (N=275 participants): A “typical dental strategy” consisting of ART + FV**

Atraumatic Restorative Treatment (ART) will be a modification of the approach used by Lo and colleagues (2006), and the cavity restored at baseline with resin reinforced glass-ionomer cement (GIC) (GC Corporation, Japan).

Participants in this arm will also receive biannual topical fluoride varnish application (FluoriMax, Elevate) according to manufacturer's instructions.

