## 5 STUDY ENROLLMENT AND WITHDRAWAL

The *original* 22 housing facilities have a total of 3749 tenants 62 years and older, therefore, we will approach 1368 participants, out of whom 958 will be screened for cavities to obtain the target sample of 550 older adults (approx. 25/housing facility) who have at least one natural tooth. Only individuals with severe medical, cognitive or motor impairments will be excluded. Individuals living independently (our study population) will likely not have severe impairments. Severe medical and motor impairments preventing enrollment will be those which would prevent the individual from completing the dental screening. Severe cognitive impairment will be determined through the consent process. If an individual is unable to explain back to the person obtaining consent what the study involves and what they will do, they will not be consented. Recruitment efforts for the main trial will take place over a two-year period. The study staff will approach tenants at various venues and inquire if they are completely edentulous to check study inclusion/exclusion criteria. Following are the estimates based on our prior study: 73% had at least one tooth; 70% providing consent; 58% with untreated caries. We expect a target of 550 participants to be randomized to the two arms.

The recruitment for all housing sites will follow a 2-stage process: (1) all participants consented will participate in the dental screening; (2) participants found to have non-urgent cavities at the screening and who fulfill the inclusion criteria will be enrolled into the clinical trial.

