### 5.2 Subject Exclusion Criteria

Following the dental screening, further exclusion criteria for non-eligibility to participate in the RCT include:

- Sensitivity to silver or other heavy-metal ions
- Those with ulcerative gingivitis or stomatitis which prevents them from receiving study treatment
- Serious life-threatening medical disease

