### 7.1 **Baseline Visit ( $T_0$ ) (Day -30 to 14)**

#### **Recruitment/Enrollment**

Study staff will recruit potential participants at the 22 participating housing facilities in coordination with the housing service coordinators and by using an in person approach at venues scheduled at the housing facility.

- Service coordinators will be provided with an introductory letter/flyer containing study information to be given to tenants and to be posted in public areas of the facility and will arrange an informational meeting for tenants (study dentist will give a talk on the interventions as suggested by our stakeholders).
- Service coordinators will arrange in-person recruitment meetings for study staff to present information regarding the study at scheduled group events (e.g. tenant meetings, health fairs, study informational presentations). For planning purposes, service coordinators will have a sign-up sheet for those interested in the sessions. At the conclusion of the session, study staff will meet individually with those interested to:
  - Review inclusion/exclusion criteria to determine eligibility (**Refer to Sections 5.1, 5.2**) utilizing the Screening and Eligibility Form
  - Obtain informed consent by reviewing the written consent form (Refer to Section 15.3) with the potential participant; ensuring comprehension of the study and

procedures, answering any questions, signing the consent form acknowledging that informed consent was reviewed and obtaining subject signature acknowledging consent was obtained. Consent will be obtained one time prior to the initiation of any study activities and will remain in effect for the duration of the study.

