### **Baseline Dental Exam**

- Dentists will administer the Safety Questionnaire (Pre-Exam).
- Hygienists will perform initial dental exam examination at participant's respective housing facility to determine eligibility to continue in the clinical trial based on caries status.
- Study staff will record results of dental exam examination.
- Hygienists, under the direction of the study dentist, will proceed as follows:
- If the participant has an urgent cavity or another serious dental problem, they will be instructed to go for dental care immediately and their participation will end.
- If the participant has no cavities or other urgent problems, they will be instructed to continue regular visits with their dentist and their participation will end.
- If the participant has cavities that require treatment but no urgent problems, they will receive one of two treatments at this visit and will continue to participate in the research. Hygienists will administer the intervention treatment (based on study arm) to all untreated active root or coronal carious lesion with ICDAS-II lesion severity code of 3 or greater.
- If a participant reports any issue with the applied treatment within one week of the treatment date, the study team will return to the housing facility to examine and correct the treated tooth as needed. Within 48 hours, the study team will call the participant to ask the participant if the issue has been resolved and will administer a paper safety questionnaire. The completed paper safety questionnaire will be stored in the CRF folder and documentation of the return visit/treatment will be added to the participant's electronic record.

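### Section 2.3.1 names fluoride hypersensitivity as a risk of SDF, but the only sensitivity exclusion in 5.2 covers silver and other heavy metals, so a fluoride-sensitive person is eligible as written

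*Combined protocol and SAP*

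**What the plan says.** Section 2.3.1 (Potential Risks) says of the Arm 1 product: "There is risk of hypersensitivity to silver or fluoride from the 38% SDF". The same section describes ART and fluoride varnish as carrying minimal risk.

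Section 5.2 has three exclusions. One concerns sensitivity: "Sensitivity to silver or other heavy-metal ions". The other two are ulcerative gingivitis or stomatitis that prevents treatment, and serious life-threatening disease.

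Section 7.1 (Recruitment/Enrollment) has staff use the Screening and Eligibility Form to "Review inclusion/exclusion criteria to determine eligibility", with a reference to 5.1 and 5.2.

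Entry rules also appear elsewhere. Section 4.1 says: "Only those with severe medical, cognitive or motor impairments will be excluded". Section 5 narrows this: "Severe medical and motor impairments preventing enrollment will be those which would prevent the individual from completing the dental screening". Sections 4.1 and 5 require at least one natural tooth. Section 7.1 (Baseline Dental Exam) ends participation under the condition "If the participant has an urgent cavity or another serious dental problem".

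On application, Section 4.2 has SDF given "following manufacturer's instructions and guidelines published by UCSF". For Arm 2 it says: "Participants in this arm will also receive biannual topical fluoride varnish application (FluoriMax, Elevate) according to manufacturer's instructions". Section 6.1 identifies that varnish as sodium fluoride.

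**The concern.** One sentence names two hypersensitivities for one product. The eligibility criteria act on silver and leave out fluoride, and no reason is given for the difference. Staff who follow 5.1 and 5.2 as written would admit a person with a risk that the protocol itself attributes to the Arm 1 product.

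Timing adds to this. Under 7.1, treatment is given at the same visit as the baseline exam that settles eligibility, so a question about fluoride is useful only if it is asked before that application.

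What is at stake is the safety of a few participants at most. It does not touch the non-inferiority comparison.

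**Working it through.** No power or estimation arithmetic applies. The check sets the named risk beside every visible entry rule and asks whether any of them covers fluoride sensitivity.

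| Where | Rules | Number | Name silver | Name fluoride |
|---|---|---|---|---|
| 5.1, first stage | consent; willingness and availability; age; residence | 4 | 0 | 0 |
| 5.1, second stage | active lesion, ICDAS code 3 or above | 1 | 0 | 0 |
| 5.2 | metal sensitivity; ulcerative gingivitis or stomatitis; life-threatening disease | 3 | 1 | 0 |
| 4.1 and 5 | at least one natural tooth | 1 | 0 | 0 |
| 4.1 and 5 | severe impairment: medical, cognitive, motor | 3 | 0 | 0 |
| 7.1, baseline exam | urgent cavity or other serious dental problem | 1 | 0 | 0 |
| Total | 4 + 1 + 3 + 1 + 3 + 1 | 13 | 1 | 0 |

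So 1 of the 2 hypersensitivities named in 2.3.1 has a matching exclusion. These counts describe wording, not harm.

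**Could a broader rule cover fluoride?** The severe-medical rule cannot, because Section 5 ties it to being unable to complete the dental screening. Section 6.6 asks about fluoride products, but for the validity of results, and it says there are no medication exclusions.

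**Could another safeguard cover it?** Six are visible:

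- Manufacturer's instructions (4.2). The content is not reproduced.
- The pre-exam Safety Questionnaire, given by dentists at both treatment visits (7.1, 7.2). Section 8.1.1 describes it as covering 15 main adverse events and does not mention allergy history. Its items are not shown.
- A consent form that describes the risks (14.3). It is not shown.
- Dentist supervision at treatment visits (6.8).
- The dentist's health-history review before the participant enters the treatment area. It appears only in the temporary COVID-19 procedures of Section 7.
- The 5.5.1 clause that lets the investigator end participation when a medical condition makes continuing contrary to the subject's best interest.

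None of these states a fluoride rule in the visible text. Whether the unseen forms or instructions contain one is unknown.

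**Exposure.** Section 6.11 gives SDF (Arm 1) or varnish (Arm 2) at baseline and at 26 weeks. A new participant is due 2 applications. A participant already treated at baseline is due at most 2 − 1 = 1 more.

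**The case against.** A named risk need not become an exclusion. Section 2.3.1 is a disclosure section. It also names staining of gums, mucosa and tooth-colored fillings, and no criterion matches that. Disclosed risks are handled by consent, dentist supervision, the pre-exam questionnaire and the safety call after treatment. A dentist who learned of a fluoride allergy from the health history, or an investigator using 5.5.1, could act without any new line. On this view only a wording mismatch has been shown, and enrollment may already be over.

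Much of this stands. The mismatch is in the text, and a failure in practice has not been demonstrated. What does not follow is that the safeguards make the line redundant. They apply equally to silver, yet the protocol still has a silver exclusion. The best-interest clause and the history review also depend on discretion, and the safety call comes after the exposure.

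Three stronger readings are tempting, and the documents support none of them. A reader might infer that fluoride-sensitive people are being treated unscreened; the screening form, questionnaire items and manufacturer's instructions are not shown, so this cannot be said. A reader might infer that the protocol names the same risk for the varnish; it ties the risk to SDF and rates varnish as minimal risk. A reader might infer an effect on the results; nothing in the documents points to one.

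**Conclusion.** The point holds as a minor patient-safety inconsistency: as written, a fluoride-sensitive person who otherwise qualifies is eligible. The number affected cannot be estimated, because the documents give no frequency.

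The conclusion rests on the ordinary reading that fluoride is neither silver nor a heavy-metal ion, and on the visible text alone. If an unseen form already asks about fluoride, the practical gap closes and only the wording of 5.2 remains to be aligned.

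Applying the rule in Arm 2 is an inference from two facts. The varnish is sodium fluoride (6.1), and facilities are randomized before recruitment begins (Section 7), so a rule used in one arm only would make eligibility differ between arms.

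**What to change.** 1. Amend the first bullet of 5.2 to read: *Sensitivity to silver, other heavy-metal ions, or fluoride*. Do not insert the word *known*; the present bullet has no such qualifier, and adding one could narrow the silver exclusion. Apply the amended bullet in both arms.

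2. Confirm that the Screening and Eligibility Form or the pre-exam Safety Questionnaire asks about fluoride sensitivity before any application. Add one question if neither does.

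No further text is needed for sensitivity that comes to light after enrollment. Section 5.5.2 already recognizes stopping the study intervention as distinct from withdrawal and requires it to be documented. Section 5.5.1 permits termination but does not compel it, and the intent-to-treat rule in 11.4 analyzes people by randomized group whatever treatment they received. Together these largely cover withholding the product while keeping the participant in the analysis.

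The cost is one amended line, at most one added question, and IRB review of the amendment (14.2). Some people would be excluded; the number is probably small but cannot be estimated. The entry for version 14.0 in the revision history refers to sites where enrollment was completed. If enrollment is complete throughout, the 5.2 change reaches no new participant. The benefit is then limited to 26-week applications still due, in people who have already had one application and were due a safety call after it.
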